4.5. Dose Justification

4.5.1. GSK3196165

- The dosing regimen for this study includes five subcutaneous (SC) loading doses of GSK3196165 180 mg administered every week, followed by three doses of 180 mg SC administered every other week. The predicted PK plasma profile of GSK3196165 using this dosing regimen is shown in Figure 2 below. This regimen was selected to i) produce sufficient drug exposure in both plasma and synovial fluid to inhibit free GM-CSF from binding to its receptor, and ii) be associated with an appropriate margin to the no observed adverse effect level (NOAEL) and the no observed effect level (NOEL) (the dose at which foamy alveolar macrophages were not observed in the 13-week cynomolgus monkey study; see IB (GSK Document Number 2014N190256_01).
- The predicted exposures associated with the proposed dosing regimen over 10 weeks, allows a 30-fold margin to the NOAEL and a 10-fold margin to the NOEL in preclinical studies of similar duration. In addition, a dose of 180 mg SC is predicted to result in steady-state exposures which will allow an approximate 26-fold margin to the NOAEL, and a three-fold margin to the NOEL based on the

findings in the 26-week monkey study. Of note, in the monkey 26-week study, full reversibility of the foamy alveolar macrophages was observed following clearance of GSK3196165. The IV 4-week monkey study provides additional safety cover for the weekly loading dosing phase of the proposed clinical study (Table 1).

Figure 2 Predicted GSK3196165 Plasma Concentrations at the Recommended Dosing Regimen (Median and 95% Confidence Interval)

Table 1Safety Margins with 180 mg SC GSK3196165 Relative to Exposures
in Non-clinical Toxicology Studies

Study	Species	Assessment	Dose (mg/kg/wk)	AUC(₀-336) µg.hr/mL⁵	Fold difference vs . QW (end of weekly dosing phase)	Fold difference vs. every other week dosing (steady state)
Repeat Dose	Dhaarra		5	8814	3.5	
Toxicology,	Rnesus	Week 4	25	44500	18	Not applicable
4 weeks IV	WOIKEy		100 ^{c,d}	110201	44	
Repeat Dose			10	7124	2.8	3.8
Toxicology,	Monkey	Week 13	30 ^d	25870	10	14
13 weeks SC	Monitoy		100°	75594	30	40
Repeat Dose			5 ^d	5704	2.3	3.0
Toxicology,	Rnesus Monkey W	Week 26	15	22528	9.0	12
26 weeks IV	Workey		50°	48734	19	26
MSC-1000 and		End of weekly dosing phase Days 28-42	180 mg weekly x5 SC	2515		
MOR103C10 4 single dose (IV & SC)ª	Human	Every other week at steady state Days 140-154	180 mg every other week SC	1873		

- AUC₍₀₋₃₃₆₎=Area under drug concentration time curve from time zero to 336 hours postdose; IV intravenous; QW=once a week; SC subcutaneous
- a. Simulated mean area under the plasma concentration time curve (AUC) based on analysis of SC and IV data for doses ≥0.5 mg/kg from study MSC-1000 (N=18) and study MOR103C104 (N=32) with a two compartment model and calculation of F by ratio of intravenous plasma clearance/subcutaneous plasma clearance (Cl_{IV}/Cl_{SC}) with bioavailability of 44% (95% Cl 37%-53%)
- b. As there were no significant differences on sampling occasions or gender differences within each primate study, the end of study mean area under drug concentration time curve from time zero to 168 hours postdose (AUC_[0-168]) values have been used and multiplied by two to obtain mean concentrations over a two-week period
- c. No observed adverse effect dose level (NOAEL)
- d. No observed effect dose level (NOEL)

4.5.2. Placebo

Placebo control (on methotrexate background) is required for this study in order to provide an adequate internal control and reference group for the analysis of changes in biomarkers. This is of particular importance given the exploratory nature of the biomarker tests being used in this study.

Both the 3:1 randomization ratio and the treatment duration of 10 weeks will minimize the exposure to placebo in the study. If a subject experiences an unacceptable level of disease activity during the study, the investigator may withdraw the subject at any point.

4.5.3. Methotrexate Background

All subjects will continue to receive MTX (and folic or folinic acid) throughout the study.

4.6. Benefit:Risk Assessment

Since GSK3196165 is still in early development with limited efficacy and safety data available, an integrated benefit/risk evaluation has not been performed at this point in time. However, summaries of findings from both non-clinical and clinical studies conducted with GSK3196165 can be found in the IB (GSK Document Number 2014N190256_01). The following section outlines the potential risk assessment and mitigation strategy for this protocol.

	 A recent study has reported that individual auto- antibodies from patients only partially-neutralized GM-CSF and when injected into mice together with human GM- CSF led to the accumulation 	Number 2014N190256_01) for further details). Therefore, the risk of development of PAP in this study is anticipated to be low.
	CSF led to the accumulation of a large pool of circulating GM-CSF that remained partially bioavailable [Piccoli, 2015]. In contrast, a combination of three non- cross-competing antibodies completely neutralized GM- CSF activity in vitro by sequestering the cytokine in high-molecular-weight complexes, and in vivo promoted the rapid degradation of GM-CSF- containing immune complexes in an Fc-	 Subject Monitoring: Specific pulmonary assessments are a requirement of the study protocol: Subjects will be assessed every visit for the development of cough and dyspnea, and will also have regular chest auscultation and pulse oximetry measurements. Persistent cough or
	dependent manner. These findings provide a plausible explanation for the severe phenotype of PAP patients and for the low likelihood of treatments based on single anti-GM-CSF monoclonal antibodies causing PAP.	 dyspnea will be reported as an AESI. Pulmonary function testing (spirometry and D_{LCO} measurements) will be performed during screening, at 12 weeks, and at the follow-up visit. Relative
	Non-clinical Data: Non-adverse minimal to mild foamy alveolar macrophage accumulation was noted in lungs of monkeys in the 13-week SC and 26-week intravenous (IV) toxicology studies, but reversed following off drug period. Dose levels at which foamy alveolar macrophages were not	 decrease in D_{LCO} >15% from screening will be reported as an AESI if confirmed with three consecutive weekly tests. In the event of any new or clinically significant pulmonary abnormalities that may develop during the

Potential Risk of Clinical	Summary of Data/Rationale	Mitigation Strategy
Significance	for Risk	
Potential Risk of Clinical Significance	Summary of Data/Rationale for Risk observed were identified in these studies. Clinical Data: No cases of PAP have been reported to date in the clinical development program. Furthermore evaluation of pulmonary function has not demonstrated any abnormalities in pulmonary functions.	Mitigation Strategy study and persist for three consecutive weeks (e.g. , increased shortness of breath/dyspnea, or unexplained and persistent coughing), the subject will be withdrawn from study drug for the remainder of the study and it is recommended that the subject be referred to a pulmonologist for further assessment. The subject should be followed until the symptoms or signs that caused referral have
		resolved and/or the diagnosis has been determined. Suggested pulmonary assessment and management algorithms will be provided in a separate Pulmonary Safety Guidance Document in
Hypersensitivity reactions, including anaphylaxis	There is a potential risk of hypersensitivity reactions, including anaphylaxis, during and following the administration of protein-based products, such as GSK3196165. Clinical Data: No allergic or acute systemic reactions have been observed to date in the clinical development program.	 Subject Selection: Subjects with a history of sensitivity to any of the study treatments, or components thereof, or a history of drug or other allergy that, in the opinion of the investigator or Medical Monitor, contraindicates their participation, will not be permitted to enter the study.
		Study Treatment Administration/Subject

Summary of Data/Rationale	Mitigation Strategy
for Risk	
	 Monitoring: All SC administrations will be performed at the clinical site. Subjects will be required to remain monitored at the site for 1 hour after the injection for the first three injections, and then for 30 minutes for subsequent injections. Subjects should be informed of the signs and symptoms of an acute hypersensitivity reaction, and be instructed to seek immediate medical care should they develop. This information will also be contained within the subject Informed Consent Form. Should hypersensitivity or anaphylaxis occur, subjects should be managed appropriately per local guidelines/medical judgment. Severe or serious hypersensitivity or anaphylaxis is categorized

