7.1. Time and Events Table

Procedures	Screening	Dees				Treatme	nt Period				FU	EW ¹
	- up to 6 Base	Base-	Week									
	weeks	IIIIC	1	2	3	4	6	8	10	12	22	
					Visi	t						
	1	2	3	4	5	6	7	8	9	10	11	
					Day	/						
		1	8	15	22	29	43	57	71	85	155	
Written Informed Consent(s)	Х											
Subject Demography	Х											
Medical, Disease, Therapy History	Х											
Inclusion/Exclusion Criteria	Х											
PRO ² and efficacy assessments ³												
Patient's Assessment of Arthritis Pain,												
Patient's Global Assessment of Arthritis,	Х	X ⁴	Х	Х	Х	Х	Х	Х	Х	Х	Х	Х
Physician's Global Assessment of Arthritis ²												
HAQ-DI ²	X	X ⁴	Х	X	Х	X	X	X	X	X	X	X
RA Symptom and Impact Diary ²	X	X ⁴	Х				X			X	Х	Х
Swollen (66) & Tender (68) Joint Count ³	X	X ⁴	Х	X	Х	X	X	X	X	X	X	X
MRI	X ²⁰					X ²¹				X ²¹	X ²¹	X22
Safety Evaluations ⁵												
Concomitant Medication	Х	X ⁴	Х	Х	Х	Х	Х	Х	Х	Х	Х	Х
Physical Examination ⁶	Х	X4								X		Х
Vital Signs	X	X	Х	Х	Х	X	X	X	X	X		
12-lead ECG ⁷	X									X		Х
AEs/SAEs ⁸	Х	Х	Х	Х	Х	Х	Х	Х	Х	Х	Х	Х
Cough, Lung Auscultation, Pulse Oximetry,	Y	Y	Y	Y	Y	Y	Y	Y	Y	Y	x	x
Borg Dyspnea Scale	^	^	^	^	^	^	^	^	^	^	^	^
Chest X-ray ⁹	X											
Spirometry (FEV1, FVC), D _{LCO}	X ¹⁰									X ¹¹	X ¹¹	X ¹¹

2015N261421_01

CONFIDENTIAL

205180

Procedures	Screening	Paga	Treatment Period							FU	EW ¹	
	- up to 6			Week								
	weeks	iiie	1	2	3	4	6	8	10	12	22	
					Visi	t						
	1	2	3	4	5	6	7	8	9	10	11	
				_	Day	1						
		1	8	15	22	29	43	57	71	85	155	
Laboratory Assessments												
Hematology, Chemistry	Х	X4		Х	-	Х		Х		X	Х	Х
TB, HBsAg, HepB cAb, HepC Ab, HIV	Х											
CRP, ESR ¹²	Х	X ⁴	Х	Х	Х	Х	Х	Х	Х	Х	Х	Х
RF, ACPA (anti-CCP)		X ⁴										
Cholesterol, triglycerides, HDL, LDL ¹³		X 4								Х	Х	Х
Pregnancy test ¹⁴	S	U				U		U		U	U	U
Urinalysis (dip stick)	Х					Х		Х		X	X	Х
Other Laboratory Assessments												
PK Sampling (GSK3196165) ¹⁵		Х	Х	Х		Х	Х	Х		X	Х	Х
GM-CSF & PD blood biomarkers	Х	X ⁴	Х	Х		Х	Х	Х		Х	Х	Х
Whole blood flow cytometry		X 4	Х			Х				X	Х	Х
RNA		X ⁴								Х	Х	Х
PGx sampling DNA ¹⁶		X ⁴										
Lung biomarkers ¹⁷		X ⁴								Х	Х	Х
Anti-GM-CSF auto-antibodies ¹⁷		X ⁴										
Immunogenicity ¹⁸		X4		Х		Х				X	X	X
Study Treatment GSK3196165/placebo ¹⁹		V	v	X	X	X	X	X	v			
(Niethotrexate and folic acid weekly throughout treatment with GSK3196165)		X	X	X	X	X	X	X	X			

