- 9. Unless performed within previous 12 weeks (no repeat if subject re-screened).
- 10. If $D_{LCO} \ge 60\%$ but <70\% predicted, a chest HRCT must be performed. If this cannot be done within the screening window, then the subject must be re-screened.
- 11. Consider repeat DLCO if >15% relative decrease from baseline (recommendations provided in the Pulmonary Safety Guidance document).
- 12. ESR measured locally.
- 13. >8h fasting required before blood draw.
- 14. For women of child-bearing potential. S=serum; U=urine.
- 15. Blood samples taken before dosing.
- 16. In consenting subjects.
- 17. To be analyzed at end of study or in event of pulmonary safety signal.
- 18. In addition to these scheduled immunogenicity assessments, "event-driven" testing (see Section 7.8) will also be employed for those subjects that experience anaphylaxis, serious hypersensitivity, or adverse events related to study drug administration that led to withdrawal from the study.
- 19. GSK3196165 or placebo must be administered on the same day each week ±1 day for the first 5 weekly doses, thereafter on the same day every other week (EOW) ±3 days.
- 20. Subjects must have passed all screening assessments, including laboratory tests, prior to undertaking MRI scanning.
- 21. MRI may be performed up to 7 days after scheduled visit.
- 22. MRI should be performed at Early Withdrawal visit if previous MRI was done >14 days before.

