7.6.6. Adverse Events of Special Interest

Please see Section 4.6.1 for a discussion of potential risks with GSK3196165. AEs of special interest include:

- Serious infections, including serious respiratory infections and TB.
- Opportunistic infections.

- Neutropenia (grade 3 or 4).
- Respiratory events including:
 - Persistent (for 3 consecutive weeks) reduction in D_{LCO} >15%
 - Persistent (for 3 consecutive weeks) cough and/or dyspnea
 - Non-life-threatening pulmonary changes related to surfactant accumulation.
- PAP.
- Hypersensitivity reactions, including anaphylaxis.
- Injection site reactions.
- Persistent cough or dyspnea.

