7.6.12. Pulmonary Assessments

Pulmonary assessments are a key aspect of the safety monitoring in this study.

The following pulmonary assessments will be performed at the time points presented in the Time and Events Table (Section 7.1).

- Chest X-ray.
- Cough.
- Borg dyspnea questionnaire.
- Lung auscultation.
- Pulse oximetry.
- PFTs spirometry (FEV1, FVC), gas transfer (D_{LCO}).

PFTs should be performed according to 2005 ATS/ERS recommendations for lung function testing [MacIntyre, 2005; Miller, 2005a; Miller, 2005b]. Spirometry should be

performed prior to D_{LCO} testing. The standards for acceptable testing sessions are described further in the Pulmonary Safety Guidance document in the SRM.

In the event of any new or clinically significant pulmonary abnormalities that may develop during the study (*e.g.*, increased shortness of breath/dyspnea, or unexplained and persistent coughing; or >15% relative decrease in D_{LCO} from baseline), it is recommended that the subject be referred to a pulmonologist for further assessment. The study treatment should be suspended until the symptoms or signs that caused referral have resolved and/or the underlying diagnosis has been determined and clinically significant events have been excluded by the pulmonologist. Suggested pulmonary assessment/management algorithms are provided in a separate Pulmonary Safety Guidance Document in the SRM.

Additional pulmonary imaging (HRCT) or other tests may be performed on a subject during the study to investigate pulmonary abnormalities, and the SRT may request copies of any reports or images for central review.

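### The DLCO adverse event of special interest rests on weekly repeat tests that the protocol leaves discretionary, so a fall that is not repeated is not counted under it

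*Protocol*

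**What the plan says.** AESI incidence is part of a secondary safety endpoint (Protocol Section 3). For DLCO, the AESI is worded in two places. The risk table in Section 4.6.1 takes a relative decrease of more than 15% from screening and says that it "will be reported as an AESI if confirmed with three consecutive weekly tests". The list in Section 7.6.6 reads "Persistent (for 3 consecutive weeks) reduction in" DLCO of more than 15%, without a reference value and without mentioning weekly tests.

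On timing, Section 4.6.1 says that pulmonary function tests "will be performed during screening, at 12 weeks, and at the follow-up visit". The Time and Events Table (Section 7.1) agrees and adds the early withdrawal visit. Footnote 11, attached to the three post-screening entries, reads "Consider repeat DLCO if >15% relative decrease from baseline" and refers to recommendations in the Pulmonary Safety Guidance document, which belongs to the Study Reference Manual and is not shown.

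Section 7.6.12 recommends referral to a pulmonologist for new or clinically significant lung abnormalities and gives a DLCO decrease above 15% as one example. It continues: "The study treatment should be suspended until the symptoms or signs that caused referral have resolved". It does not ask for weekly DLCO tests.

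**The concern.** The definition presumes a run of weekly tests, while the schedule and its footnote make any repeat a matter of judgement. Whether a given fall becomes an AESI then depends partly on whether the site repeated the test. A subject with a large fall at Week 12 and no further test until Week 22 does not meet the definition. Under the AESI count, that subject looks the same as one whose repeat tests returned to normal.

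Pulmonary toxicity is one of the key potential risks that the protocol names for this mechanism (Section 4.6.3), and Section 7.6.12 treats lung assessment as central to safety monitoring. If the count of DLCO AESIs is low or zero, a reader cannot tell from that count alone whether falls were absent, were repeated and not confirmed, or were never repeated.

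**Working it through.** The protocol states no figure for this point, so the check is schedule arithmetic and a comparison of sections.

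**Inputs.** Section 7.1 gives the last dose at Week 10 (Day 71) and DLCO at Week 12 (Day 85), Week 22 (Day 155) and early withdrawal. Sections 4.6.1 and 7.6.6 give the three-week rule. Section 7.6.4.1 says that adverse events are collected until the follow-up contact 12 weeks after the last dose. Section 9.2.1 assumes 30 subjects on GSK3196165 and 10 on placebo.

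1. **Completers.** The two scheduled post-screening tests are 155 − 85 = 70 days, or 10 weeks, apart. Three weeks is 21 days, so any three-week window holds at most 1 scheduled test, against 3 required.

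2. **Early stoppers.** A subject who stops treatment but stays on study can have three tests: early withdrawal, Week 12 and Week 22. Because the last two are 70 days apart, a three-week window holds at most 2. The early withdrawal test does not supply the confirmation.

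3. **Fall first seen at Week 12.** Weekly tests fall on Days 85, 92 and 99 if the first test counts, or on Days 92, 99 and 106 if three further tests are meant. The wording does not settle which. All but Day 85 are unscheduled.

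4. **Fall first seen at Week 22.** The corresponding days are 155, 162 and 169, or 162, 169 and 176. For a completer, routine collection closes at Day 71 + 84 = Day 155, so confirmation falls after the last scheduled visit and after that window.

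5. **Weight of one subject.** One subject is 1/30 = 3.3% of the active arm and 1/10 = 10% of the placebo arm, so a single unrepeated fall changes the observed incidence visibly.

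6. **Suspension example.** The first scheduled post-screening test comes 85 − 71 = 14 days after the last dose. The early withdrawal test follows discontinuation (footnote 1 of Section 7.1). No scheduled DLCO test can therefore lead to suspension of treatment.

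7. **Reference value.** Section 4.6.1 compares with screening, while footnote 11 and Section 7.6.12 compare with baseline. The only pre-treatment DLCO is the screening one, so this is a difference in wording only.

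**The case against.** The strongest reply is that confirmatory tests are normally event-driven and are not entered as fixed visits. That is right. A reader might infer from the schedule that the DLCO AESI can never be met, or that its count must be 0 of 40. The protocol does not support this: a zero from scheduled tests alone is close to true by definition, and unscheduled repeats can satisfy the rule. The guidance document may also describe weekly repeats. Even so, footnote 11 calls its content recommendations and Section 7.6.12 calls its algorithms suggested, so nothing in the protocol makes the repeats a requirement.

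It can also be said that a fall is not lost if it misses AESI status. This stands too. Section 7.6.5 has abnormal safety assessments judged clinically significant recorded as adverse events, Section 7.6.3 lists DLCO among the safety assessments, and cough, oximetry and dyspnea are checked at every visit. A reader might infer that the protocol counts missing confirmation as no event in all safety reporting. It states no such rule; the consequence is confined to the DLCO part of the AESI count.

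For Week 22, Section 4.6.1 foresees following a referred subject until resolution or diagnosis. That softens the gap, but the sentence concerns abnormalities that have already persisted for three weeks. It does not call for weekly DLCO tests or say whether confirmation after the follow-up visit counts.

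On suspension, a reader might infer a failed safeguard. That goes too far: the DLCO fall is one example among several triggers, the others are assessed throughout dosing, and Sections 7.6.2 and 7.6.12 allow added tests.

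Finally, tabulations are properly left to the analysis plan, which may already cover this one. An analysis plan cannot supply repeat tests that were never done, nor reconcile protocol sections with each other.

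**Conclusion.** The concern holds in a limited form. Sections 4.6.1 and 7.6.6 make AESI status depend on confirmation over three consecutive weekly tests or weeks, and footnote 11 makes the confirming tests discretionary. Following the protocol as written, an unrepeated fall above 15%, including one first seen at Week 22, is not counted as this AESI, although it may be captured elsewhere in the safety data.

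In terms of the schedule, at most 1 of the 3 required tests is scheduled in any three-week window for a completer, and at most 2 for a subject who stops treatment early and stays on study. The number of events missed cannot be calculated: the protocol gives neither an expected rate of DLCO falls nor a rate of repeat testing. Investigators are blinded (Section 6.4), so there is no evident reason for repeats to differ systematically between arms. The likely effect is under-ascertainment that varies by site, with chance imbalance mattering because the arms are small.

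This rests on two assumptions: that the guidance document does not bind sites to weekly repeats, and that the AESI is counted as Sections 4.6.1 and 7.6.6 define it. The suspension wording in Section 7.6.12 is a minor inconsistency.

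**What to change.** 1. Alongside the AESI count, report by arm every subject with a relative DLCO decrease above 15% from screening at Week 12, Week 22 or early withdrawal. Split these into confirmed, not confirmed on repeat, and not repeated, so that an absent repeat is not treated as no event. This is one table, which can sit in the analysis plan. It uses data already collected, provided that unscheduled DLCO results are entered in the database.

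2. Reconcile footnote 11 of Section 7.1 with the confirmation required in Sections 4.6.1 and 7.6.6. State one wording of the definition, whether the first abnormal test counts toward the three, and how a fall first seen at Week 22 is classified given when adverse event collection ends. The cost is a protocol clarification, plus whatever repeat tests the definition already presumes in the subjects who trigger it.

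3. As a minor point, reconcile the DLCO example in the suspension text of Section 7.6.12 with the schedule in Section 7.1, which has no DLCO test during dosing. This is a wording change.

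How the sections are reconciled is for the sponsor to decide; no clinical rule is proposed here.

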5.5. Treatment Interruption

5.5.1. Respiratory Symptoms

Study medications will be temporarily suspended to allow investigation in the event of any of the following:

• Persistent cough (common terminology criteria (CTC) grade 2 or 3) or dyspnea (Borg scale grade 3 or above) for three consecutive weeks. Details on CTC and Borg scale are provided in the SRM.

The subject should be referred to a pulmonologist for further assessment. The study drug should be suspended until the symptoms or signs that caused the referral have resolved and/or the diagnosis has been determined and clinically significant events have been excluded by the pulmonologist. As described in Section 5.4, a confirmed diagnosis of PAP necessitates permanent cessation of study medication and withdrawal of the subject from the study. Suggested pulmonary assessment and management algorithms are provided in a separate Pulmonary Safety Guidance Document in the SRM.

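### After three weeks of respiratory symptoms, Section 4.6.1 bars any restart of study drug while Sections 5.5.1 and 7.6.12 only suspend it, and the three triggers differ

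*Protocol*

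**What the plan says.** Three current sections of the Protocol govern dosing when respiratory symptoms appear.

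- **Section 4.6.1 (Risk Assessment, PAP row, mitigation column).** The rule opens with "In the event of any new or clinically significant pulmonary abnormalities that may develop during the". After a table break it sets a duration condition, "study and persist for three consecutive weeks", and gives dyspnea and unexplained persistent cough as examples. The consequence is that "the subject will be withdrawn from study drug for the remainder of the study". Referral to a pulmonologist is recommended.
- **Section 5.5.1 (Respiratory Symptoms, under Treatment Interruption).** The action comes first: "Study medications will be temporarily suspended to allow investigation in the event of any of the following". The one trigger that the section then lists is graded and has a duration: "Persistent cough (common terminology criteria (CTC) grade 2 or 3) or dyspnea (Borg scale grade 3 or above) for three consecutive weeks". The stop is conditional: "The study drug should be suspended until the symptoms or signs that caused the referral have resolved and/or the diagnosis has been determined", and the pulmonologist must also have excluded clinically significant events. The section adds that "a confirmed diagnosis of PAP necessitates permanent cessation of study medication".
- **Section 7.6.12 (Pulmonary Assessments).** It applies to "any new or clinically significant pulmonary abnormalities that may develop during the study". It gives the same dyspnea and cough examples, adds a relative fall in DLCO of more than 15%, and suspends treatment on terms close to those of 5.5.1.

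Section 5.4 lists confirmed PAP among the reasons for discontinuation and refers to 4.6.1 for it. It does not list persistent cough or dyspnea.

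**The concern.** Sections 4.6.1 and 5.5.1 both act at three consecutive weeks of cough or dyspnea and prescribe different outcomes. One ends study drug for good; the other pauses it and allows a restart. Two sites that each follow a current section could therefore differ on whether the same subject may be exposed to the drug again.

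Section 4.6.3 names pulmonary toxicity among the key potential risks, and the Time and Events Table schedules cough and dyspnea assessment at every visit, so the rule operates throughout treatment. Cough has been seen with this drug: Section 2.1.4 reports 0 of 27 placebo and 3 of 69 active subjects in an earlier study. Those are cough reports of any kind, not three-week events.

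The visit path can split as well. Footnote 1 of the Time and Events Table requires an early withdrawal visit after premature discontinuation of study medication, and footnote 22 adds an MRI if the last scan was more than 14 days earlier. That path follows from 4.6.1, but not from a suspension that ends in a restart. In a study of about 40 subjects, exposure, visit timing and MRI timing could then depend on which section a site reads.

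**Working it through.** **1. The rules side by side**

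| | Section 4.6.1 | Section 5.5.1 | Section 7.6.12 |
|---|---|---|---|
| Duration | three consecutive weeks | three consecutive weeks | none stated in general; cough is called persistent, dyspnea has no duration |
| Severity | no grade | CTC grade 2 or 3 cough, or Borg 3 or above dyspnea | no grade |
| Study drug | stopped for the rest of the study | suspended | suspended |
| Restart | not allowed | possible after resolution and/or diagnosis, with significant events excluded | same as 5.5.1 |

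**2. Three test cases**

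- *New, unexplained grade 2 cough for three weeks.* All three sections are met. 4.6.1 rules out a restart; 5.5.1 and 7.6.12 allow one.
- *New, unexplained cough below grade 2 for three weeks.* 4.6.1 stops drug permanently. 5.5.1 does not act. 7.6.12 suspends, since it has no grade.
- *New dyspnea lasting less than three weeks.* Neither 4.6.1 nor 5.5.1 acts. 7.6.12 suspends.

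Any event that meets 4.6.1 also falls within the wording of 7.6.12. No section states which prevails.

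**3. Reach in doses, 4.6.1 against 5.5.1**

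Inputs from the Time and Events Table (Section 7.1):
- Doses fall on Days 1, 8, 15, 22, 29, 43, 57 and 71, which is 8 doses.
- Footnote 5 puts safety evaluations before dosing, so the dose at the detection visit is withheld under both rules. It is assumed not to be made up.
- The earliest possible detection is onset on Day 1 with the criterion met on Day 22 (22 − 1 = 21 days).

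Total under 4.6.1 = doses already given. Ceiling under 5.5.1 = doses already given + doses scheduled after the detection visit.

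| Criterion met | 4.6.1 | 5.5.1 ceiling | Gap | Days to next dose |
|---|---|---|---|---|
| Week 3 (Day 22) | 3 | 3 + 4 = 7 | 4 | 29 − 22 = 7 |
| Week 4 (Day 29) | 4 | 4 + 3 = 7 | 3 | 43 − 29 = 14 |
| Week 6 (Day 43) | 5 | 5 + 2 = 7 | 2 | 57 − 43 = 14 |
| Week 8 (Day 57) | 6 | 6 + 1 = 7 | 1 | 71 − 57 = 14 |
| Week 10 (Day 71) | 7 | 7 + 0 = 7 | 0 | none left |

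The ceiling is reached only if the subject is cleared before the next scheduled dose, so each gap is a maximum.

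**4. Follow-up timing for the Week 3 case**

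Follow-up falls 12 weeks (84 days) after the last dose.
- Stopped for good, last dose Day 15: 15 + 84 = Day 99, as the earliest date.
- Resumed, last dose Day 71: 71 + 84 = Day 155.

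**The case against.** Several points can fairly be made on the other side.

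- **Section 7.6.12 need not contradict 4.6.1.** With no stated duration, it could be a first step (suspend and refer), with 4.6.1 as the second (stop if symptoms last three weeks). The wording permits this, although 7.6.12 sets its own end to the suspension. The reading does not help 5.5.1, whose suspension begins at three weeks, the point at which 4.6.1 already rules out a restart. The sharpest conflict is therefore 4.6.1 against 5.5.1.
- **Section 4.6.1 is a risk summary, and the stopping rules sit in Section 5.** Sections 5.4, 5.5.1 and 7.6.12 are compatible with one another, which leaves 4.6.1 as the outlier. But 4.6.1 is worded as a directive and Section 5.4 refers to it. Amendment 01 also edited this very rule, removing the DLCO trigger because the second DLCO test comes after dosing has ended. The sponsor thus treated it as governing dosing.
- **A restart under 5.5.1 is not automatic.** It needs specialist clearance. The section does not say that PAP is the only ground for a permanent stop, and Section 5.4 lets the investigator withdraw a subject for safety at any time. This stands and narrows the practical gap.
- **The dose gap is a best case for restarting.** This also stands. In addition, 7.6.12 could have suspended dosing before Day 22, so the count of 3 doses already given need not hold if that section is followed.
- **A Pulmonary Safety Guidance Document exists in the Study Reference Manual.** Its content is not in the Protocol. The Protocol describes its algorithms only as suggested, so they cannot settle a conflict between protocol requirements.

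**Conclusion.** The concern holds. For a new, unexplained cough of grade 2 lasting three weeks, current Protocol text gives incompatible instructions on restarting study drug: 4.6.1 forbids it and 5.5.1 allows it. Section 7.6.12 sides with suspension, but that conflict is weaker because the section has no general duration. The triggers also differ, so a lower-grade symptom of three weeks can end treatment under 4.6.1 without reaching the threshold in 5.5.1.

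Both rules stop dosing at detection, so what is at issue is later re-exposure and the visit path. The difference is at most 4 of 8 doses at Week 3, falling to 0 at Week 10. For the Week 3 case, follow-up falls as early as Day 99 or on Day 155. These figures assume visits on nominal days, no missed doses, the detection-visit dose not made up, and clearance before the next dose. How many subjects would meet the criterion cannot be estimated from the Protocol.

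This must be fixed, because it is a contradictory stopping rule for a risk that the Protocol itself names as key.

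**What to change.** Reconcile Sections 4.6.1, 5.5.1 and 7.6.12 so that they agree on three things: the trigger, including whether a severity grade applies; the duration; and the consequence, including whether a restart is allowed. Then check that the Section 5.4 reference to 4.6.1 is consistent with the result, and that it is clear when the early withdrawal visit in footnote 1 applies. Which rule to adopt is a decision for the sponsor's medical team.

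The cost is a protocol clarification or amendment to a few sentences in three sections. Sample size, visit schedule and analysis do not change.
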